The intervention will be followed by a 4-week and 1-year **follow-up** period. At the end of each follow-up (T= 12, and 60 weeks), the participants will collect a stool sample for the same measurements as those at the end of the intervention period (fecal calprotectin level, microbiota composition, and SCFAs profile), and complete the questionnaires including P-SCCAI (once a week). Information of medication use will be extracted from patient record and diary (once a week).

As the intervention will take place at home, the study can be conducted in a merely coronavirus (COVID-19)-proof setting.

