At T = 0, 4, and 8 weeks, health-related quality of life will be assessed by the SIBDQ questionnaire (see F1). SIBDQ is a 10 item shortened version of the original IBDQ which was 32 items. It has a seven-point graded scale where 1 represents very troublesome symptoms and 7 represents the absence of troublesome symptoms. Measures quality of life as measured in four domains (bowel symptoms, emotional health, systemic systems and social function) [58]. Its reliability and responsiveness to change has been validated in UC [59].

Medication use

At T= 0, 4, 8, 12 and 60 weeks, information of medication use will be extracted from patient record and diary. It consists of the current medication use (e.g., aminosalicylates, corticosteroids, immunosuppressive agents, antimicrobial agents, and inhibitors of tumour necrosis factor-alpha (TNF- α)). Medication changes at week 4, 8, 12, and 60 provide information on disease development, with a downgrade means improvement and an upgrade means worsening of UC.

Safety parameters

At T= 0, 4, and 8 weeks, safety parameters (i.e., incidence of adverse events) will be monitored by patient record and diary. In this diary, all relapse-relevant information, including the need for systemic steroids, hospitalization, and surgery will be collected.

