9.2 AEs, SAEs and SUSARs

9.2.1 Adverse events (AEs)

Adverse events are defined as any undesirable experience occurring to a subject during the study, whether or not considered related to [the investigational product/trial procedure/ the experimental intervention]. All adverse events reported spontaneously by the subject or observed by the investigator or his staff will be recorded.

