9.4 Follow-up of adverse events

All AEs will be followed until they have abated, or until a stable situation has been reached. Depending on the event, follow up may require additional tests or medical procedures as indicated, and/or referral to the general physician or a medical specialist. SAEs need to be reported till the end of study within the Netherlands, as defined in the protocol.

9.5 [Data Safety Monitoring Board (DSMB) / Safety Committee]

Not applicable.

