13.2 Synthesis

The following actions will be taken to reduce the small risks of this study:

- The following aspects point towards a safe use of the dietary prebiotic supplements:
 - They are commonly consumed throughout the world.
 - All compounds are commercially available and tested safe for human consumption.
 - Prebiotic supplements were selected on the basis of expected low GI tolerance issues.
 - Prebiotic supplements will be given in a relatively low daily dose.
 - To avoid gastrointestinal complaints, due to a sudden intake of fiber supplements during the first week, the study participants will consume only one sachet per day, followed by two sachets per day for the remainder of the study.
- The following aspects include safety monitoring throughout the study:
 - We will monitor GI complaints via questionnaires throughout the study.
 - A medical doctor has been appointed for this study to check and discuss reported AEs with the subjects.
- The following aspects point towards a low-risk patient group:
 - Only UC patients with mild disease activity are included.
 - Subjects with other digestive tract disorders that are expected to interfere with this study are excluded from participation.
- The following aspects point towards a non-burdensome sampling procedure
 - The stool sample collection aligns with their routine clinical check and will therefore not cause an extra burden.
 - We will take the applicable COVID-19 regulation into account when it comes to potential contact with the subjects (e.g., information meeting).

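### Scheduled collection of adverse events and relapse information stops at week 8, although follow-up runs to week 60 and the patient record is still reviewed at weeks 12 and 60

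*Protocol*

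**What the plan says.** Protocol section 8.1.2 (Safety parameters) fixes the schedule: "At T= 0, 4, and 8 weeks, safety parameters (i.e., incidence of adverse events) will be monitored by patient record and diary". The next sentence adds the relapse items: "In this diary, all relapse-relevant information, including the need for systemic steroids, hospitalization, and surgery will be collected". It gives no later time point for either.

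The follow-up text agrees with this. In section 3, the sentence for weeks 4 and 8 takes both medication use and adverse events from the record and diary. The corresponding sentence for weeks 12 and 60, "Information of medication use will be extracted from patient record and diary (once a week"), leaves adverse events out. The follow-up part of section 8.3 likewise lists P-SCCAI, medication use and a stool sample only.

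The safety chapter has a wider window. Section 9.2.1: "Adverse events are defined as any undesirable experience occurring to a subject during the study", and "All adverse events reported spontaneously by the subject or observed by the investigator or his staff will be recorded". Section 9.4: "SAEs need to be reported till the end of study within the Netherlands, as defined in the protocol". Section 12.5 ends the study at the last data collection, which is planned for week 60.

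**The concern.** The definition of an adverse event covers 60 weeks, but the scheduled search for such events covers 8. The follow-up year is when the supplement has been stopped, so it is when a relapse after treatment would be seen. If relapse information is not sought in that period, the follow-up rests on two P-SCCAI readings, the medication record, calprotectin, and whatever patients or staff happen to report. A between-arm comparison of relapse after week 8 would then depend partly on who volunteers information and who notices it, and a table of non-serious adverse events would mix solicited data to week 8 with unsolicited data afterwards.

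**Working it through.** The Protocol states no figure for this point, so the check compares schedules. Those below come from sections 3, 8.1.2 and 8.3.

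| Item | Wk 0 | Wk 4 | Wk 8 | Wk 12 | Wk 60 |
|---|---|---|---|---|---|
| P-SCCAI | yes | yes | yes | yes | yes |
| Medication use (record and diary) | yes | yes | yes | yes | yes |
| Faecal calprotectin | yes | no | yes | yes | yes |
| Adverse events and relapse diary | yes | yes | yes | no | no |

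**Share of the study covered.** Scheduled adverse event and relapse collection: 8/60 = 13.3% of weeks. Without it: 60 − 8 = 52 weeks, 52/60 = 86.7%.

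**What the other sources can see after week 8.**
- P-SCCAI asks about the previous week (section 8.1.1). Readings at weeks 12 and 60 describe 2 of the 52 follow-up weeks (2/52 = 3.8%), and the gap between them is 60 − 12 = 48 weeks.
- Medication use includes corticosteroids. Section 8.1.2 describes it as current use; section 10.2 says duration is also collected. A completed steroid course may therefore appear, but the text does not require it and does not link a course to a relapse.
- Serious adverse events include unplanned hospitalisation (section 9.2.2) and are reported to study end. Elective admissions are excluded there, and an outpatient steroid course would not ordinarily meet the listed criteria.
- Spontaneous reports are recorded without a time limit, but they are unsolicited.
- A reported exacerbation leads to withdrawal (section 8.4.1, no week limit). After withdrawal there is generally no follow-up (section 8.6). The text does not say that the exacerbation and its date are recorded as an outcome.

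**Blinding.** Section 8.2 unblinds investigators once the analysis of data to week 12 is complete. Patients who have not yet reached week 60 would then be observed by staff who know the allocation. How many that is depends on the recruitment period, which is not given.

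**Illustration only.** The documents give no relapse rate. Assume a constant rate r per year, 60 patients and no dropout. Expected patients with a first relapse by week t = 60 × [1 − exp(−r·t/52)].

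| r (assumed) | By week 8 | By week 60 | Share by week 8 |
|---|---|---|---|
| 0.25 | 60 × 0.0377 = 2.3 | 60 × 0.2506 = 15.0 | 15% |
| 0.5 | 60 × 0.0740 = 4.4 | 60 × 0.4384 = 26.3 | 17% |
| 1.0 | 60 × 0.1426 = 8.6 | 60 × 0.6846 = 41.1 | 21% |

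Under these assumptions about four in five first relapses or more fall after scheduled collection ends. This is not the number missed, since the other sources would find some of them.

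**The case against.** The strongest reply is that collection does not stop at week 8; only solicitation does. That is right, and it rules out several stronger readings that a reader might infer.

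- *Adverse events are collected only to week 8, and only serious ones after that.* Not supported: section 9.2.1 records all spontaneously reported or observed events without a cut-off, and section 9.4 follows all adverse events until they abate or stabilise.
- *Relapses after treatment are not counted, and steroid use and hospitalisation are not outcomes.* Not supported: medication use, with an upgrade read as worsening, is a secondary endpoint at weeks 12 and 60; P-SCCAI and calprotectin are measured at both; unplanned hospitalisation is a serious adverse event.
- *Section 13.2 contradicts the schedule.* That section says "We will monitor GI complaints via questionnaires throughout the study", while the GSRS ends at week 8. But the same section also uses the word study for the dosing period, so it is a loose term there and not a clear conflict.
- *Section 10.2 needs adverse event data at weeks 12 and 60 because it treats safety like response over time.* The same cross-reference is used for the GSRS, the SIBDQ and even baseline-only data, so it points to method and not to time points.

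It can also be said that limiting solicited adverse events to the exposure period is defensible for a low-risk food supplement, and that relapse is not a listed objective. Both are fair, and they keep the point minor. They do not explain why the relapse items are dropped at two time points where the same record is opened anyway.

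Finally, withdrawal on exacerbation could remove the very patients that a later record review is meant to find. That stands, and the fix has to deal with it.

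**Conclusion.** The point holds in a limited form. Scheduled ascertainment of adverse events and relapse information ends at week 8, while the adverse event definition and the follow-up extend to week 60. In the remaining 52 of 60 weeks (87%), non-serious adverse events, and relapses that are treated and settle between contacts, are not systematically sought and can be missed. The loss may differ between arms for patients observed after investigators are unblinded; the documents show that possibility, not that it will happen.

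This is a low-cost improvement, not a flaw in the main result. The primary endpoint is at week 8, and no sample size, power or significance level changes. The conclusion rests on the narrative in sections 3, 8.1.2 and 8.3. Table 1 and Figure 3 could not be read, so an adverse event entry at weeks 12 and 60 cannot be excluded.

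**What to change.** 1. In section 8.1.2, and in the matching follow-up text of sections 3 and 8.3, extend the safety and relapse extraction to weeks 12 and 60, within the record and diary review already done for medication. At each, record with dates since the last contact: adverse events, steroid courses, hospitalisation and surgery.
2. Reconcile this with sections 8.4.1 and 8.6, so that an exacerbation leading to withdrawal is itself recorded, with its date, as a relapse event. This concerns what is recorded and leaves the withdrawal rule as it is.
3. If Table 1 already lists adverse events at weeks 12 and 60, bring section 8.1.2 into line with it.

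Cost: a few more items per record review at two time points, with no new visit or procedure.

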8.1.3 Other study parameters

Habitual food intake

At T= 0 (baseline), habitual dietary intake of the last month will be assessed by a validated food frequency questionnaire (FFQ, see F1) via FFQ-tool, a web-based interface tool. It provides data that will be used for potential correlation analysis with other parameters.

Participants demographics and characteristics

At T= 0 (baseline), general information (e.g., sex, age, BMI, disease duration, age at diagnosis, smoking habit, UC location, type of treatment) will be collected.

8.2 Randomisation, blinding and treatment allocation

During the screening period, participants will provide a fecal sample for microbiome signature measurement. This information will be used to assign subjects to four intervention arms by block randomization. All subjects screened for the trial will be assigned a unique participant ID number. Suitable participants will subsequently be randomised to prebiotics or placebo group using an online randomisation system accessible via password-protected access.

All sachets will be uniformly packaged to ensure double-blinding. Research teams and trial participants will be blinded to the treatment group for the duration of the trial. After collection of all laboratory & questionnaire data and performing all analysis of the baseline/intervention period the study (up to the 4-week follow-up; T=12 weeks) will be unblinded for the investigators. At the end of the study (T=60 weeks), the participants will be informed of the kind of intervention they received. (only when approved in the informed consent).

8.3 Study procedures

A detailed description of procedures is shown in **Table 1**.

Table 1 Procedures

Page 1 of 1

Informed consent procedure

Informed consent procedure
One or more information meetings will be organized prior to the study. In this meeting, the investigators will explain the background, objectives and study procedures. During this meeting, there will be time for the potential research subjects to ask questions.

After the information event, subjects have two weeks to decide whether they are interested in participation or not. Research subjects who are willing to participate will receive the informed consent and the screening package which includes the P-SCCAI questionnaire and one stool collection kit. Then within one week, subjects will receive packages with corresponding products and instructions.

If COVID-19 restrictions are still in place, we would also provide the option of having online information meetings via Microsoft Teams (“Teams is designed and developed in compliance with the Microsoft Trustworthy Computing Security Development Lifecycle (SDL), <https://docs.microsoft.com/en-us/microsoftteams/teams-security-guide>”). No personal data will be collected or send via this route. If preferred, research subjects will always have the option to attend a physical meeting.

Screening

Subjects who fulfil all inclusion criteria and none of the exclusion criteria will be invited to a screening.

One stool sample will also be provided via the specific stool collectors (**Figure 4**). For female participants, pee gutters will also be provided to accurately separate stool from urine. After collection, stool material will be immediately frozen at the home freezers of the subjects, transported on dry ice (via courier) to the laboratory and subsequently frozen at -80 °C until further

Figure 4 Stool collector analysis. DNA will be isolated from part of the stool samples and subsequently be used for qPCR. Primers

targeting total bacteria and Bacteroidetes will be used to quantify the total gene copies and calculate the relative abundance of Bacteroidetes in the stool. Subjects that have a relative abundance of Bacteroidetes $\leq 10\%$ will be assigned to the predicted responders group, while those who have a relative abundance of Bacteroidetes $\geq 15\%$ will be assigned to the predicted non-responders group.

Baseline

At baseline, selected participants need to fill out several questionnaires P-SCCAI, FFQ [60], GSRS [61], Bristol stool form scale [62], stool frequency, SIBDQ [58], information of medication use and adverse events will be extracted from patient record and diary. All questionnaires can be found in F1 Questionnaires. The GSRS questionnaire provides baseline GI complaints and tolerance information. P-SCCAI provides disease activity information. FFQ provides information regarding the usual foods consumed and the frequency of consumption. Bristol stool form scale provides stool consistency information. SIBDQ provides information on health-related quality of life.

One stool sample will also be provided. The sample will undergo the same collection and storage procedures as those in the screening period. DNA will be isolated from part of the stool samples and subsequently be used for 16S rRNA gene-based microbiota profiling using NG-Tax [63]. The stool sample will be also used for measurements of fecal calprotectin using enzyme-linked immunosorbent assay (ELISA) methods [64], and SCFAs concentrations using high-performance liquid chromatography (HPLC) [65].

Dietary intervention period (8 weeks)

During the intervention period, the subjects will consume the respective supplement (3 grams/sachet) twice per day. To minimize potential GI complaints that might occur due to intake of the prebiotics/placebo supplement, there will be a gradual increase in dosage that only 1 sachet daily will be consumed in the first week of the intervention period, followed by 2 sachets daily for the remainder of the intervention. The patients will be asked to save all the empty sachets.

At T= 4, and 8 weeks, subjects will also need to complete short questionnaires on response (P-SCCAI, once a week), GI complaints and tolerance (GSRS, once a week), stool frequency and consistency (Bristol stool form scale, a 7-day record at each week), SIBDQ (once a week). Information of medication use and adverse events will be extracted from patient record and diary (once a week).

At the end of the intervention period (T= 8 weeks), the participants will provide a second stool sample for fecal calprotectin measurements, 16S rRNA gene-based microbiota profiling, and SCFAs profile analysis. We will determine response with P-SCCAI score.

At the end of the intervention period (T= 8 weeks), the participants will be asked to return everything (used and unused sachets) to the coordinating investigator to determine compliance to the study.

Follow-up period (4 weeks and 52 weeks)

During the follow-up period, participants will not take supplements anymore.

At T=12, and 60 weeks, P-SCCAI (once a week) and medication use (once a week) will be completed.

At T=12, and 60 weeks, one time stool sample will be collected at each time point. These samples will be used for fecal calprotectin measurements, 16S rRNA gene-based microbiota profiling, and SCFAs profile analysis.

We will determine response with P-SCCAI score at T= 12, and 60 weeks.

8.4 Withdrawal of individual subjects

Subjects can leave the study at any time for any reason if they wish to do so without providing a reason and without any consequences. The investigator can decide (upon consultation with the medical supervisor) to withdraw a subject from the study for urgent medical reasons, such as serious GI complaints, negative reactions upon supplement intake, etc., or when study participants have to start medication that interferes with outcomes during the study period.

8.4.1 Specific criteria for withdrawal

A subject will be withdrawn from the study in the case of serious gastro-intestinal complaints or an exacerbation of UC reported by the subjects (such as continuous diarrhea or constipation, bloating, abdominal pain).

8.5 Replacement of individual subjects after withdrawal

Not applicable.

8.6 Follow-up of subjects withdrawn from treatment

After possible withdrawal, no follow-up of research subjects will take place, except in case of withdrawal for other medical reasons.

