4.4 Sample size calculation

The primary objective of the trial is to validate the prediction that a higher response (lower mean P-SCCAI score) is induced at T= 8 weeks by the prebiotics intervention in mild UC patients with low Bacteroidetes levels (predicted responders), but not in those with high Bacteroidetes levels (predicted non-responders) in their gut. Mild UC is defined as a P-SCCAI score of 3 to 5. According to an extensive study regarding UC disease activity conducted in the Netherlands, mild UC patients have a P-SCCAI score of 3.5 ± 0.5 (Mean \pm standard deviation (SD)), and patients in remission score at 1.0 ± 0.33 (Mean \pm SD)[34, 35].

In a series of germinated barley foodstuff (GBF) intervention studies, 10 mild to moderately active UC patients received 30 grams of GBF (equals to 10 grams fiber) daily for 4 weeks [4], and researchers found a significant decrease in clinical activity index scores. In a later study, another group of 11 mildly to moderately active UC patients consuming 20-30 grams of GBF (equals to 6.66-10 g fiber) daily for 4 weeks showed similar results, with decreases in clinical activity index scores [28].

Based on two-sided statistical testing for unpaired continuous data, an $\alpha=0.05$ (chance on type-I error) and $\beta=0.10$ (chance on type-II error), and assuming a 20% difference of mean P-SCCAI score between predicted responders with prebiotics and predicted non-responders with prebiotics, it was calculated that at least 11 subjects per group are needed for the primary outcome P-SCCAI ($\mu_1=3.5$; $SD_1=0.5$; $\mu_2=2.8$). According to previous trials on prebiotics on IBD patients, a 20% of drop-out rate is commonly seen. Given that the intervention duration is 8 weeks long, followed by a 1 year follow-up, higher dropout rate (30%) is expected. To compensate for a 30% drop-out rate, 15 subjects per group are needed.

To reach inclusion of 30 predicted responders and 30 predicted non-responders, we made an estimate how many subjects we need to screen based on the earlier obtained microbial composition of stool samples from UC patients in the Ede area. Around 50% of these subjects were categorized as low Bacteroidetes subjects (predicted responders) and while 17% of them as high Bacteroidetes subjects (predicted non-responders). To include these responders we will need to screen 177 mild UC patients.

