8. METHODS

8.1 Study parameters/endpoints

8.1.1 Main study parameter/endpoint

Response (mean P-SCCAI score) between arms at T = 8 weeks:

At T = 8 weeks (the end of the intervention), the P-SCCAI score will be collected via the P-SCCAI questionnaire. As main endpoint, the mean P-SCCAI score for each arm will be determined and compared to each other to determine the difference in response at T = 8 weeks.

P-SCCAI is derived from the original SCCAI questionnaire by translating into patients' comprehensible language, and has been validated to give substantial agreement with the original SCCAI [54]. P-SCCAI refers to disease symptoms during the previous week. It contains 13 items clustered into six domains: bowel frequency (during the day), bowel frequency (during the night), urgency of defecation, blood in stool, general well-being, and a number of defined extracolonic features of UC (i.e. arthritis, erythema nodosum, pyoderma angrenosum, uveitis).

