10.1 Primary study parameter(s)

Response (mean P-SCCAI score) between arms at T = 8 weeks

To assess the response, data of mean P-SCCAI score within each arm at T = 8 weeks (after the intervention) will be obtained.

Firstly, the mean P-SCCAI score between the predicted responders with prebiotics and predicted non-responders with prebiotics will be compared by using a Student T-test if normally distributed, otherwise a Mann-Whitney U test when skewed.

Secondly, the mean P-SCCAI score between prebiotics and placebo groups within predicted responders or predicted non-responders will be compared by using a Student T-test if normally distributed, otherwise a Mann-Whitney U test when skewed.

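### Patients withdrawn for a reported UC exacerbation have no further P-SCCAI scheduled, so week-8 scores can be missing because of the outcome itself

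*Protocol*

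**What the plan says.** Three sections of the protocol govern withdrawal.

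- Section 8.4 lets the investigator decide "to withdraw a subject from the study for urgent medical reasons, such as serious GI complaints", or when a patient has to start medication that interferes with outcomes.
- Section 8.4.1 is mandatory: "A subject will be withdrawn from the study in the case of serious gastro-intestinal complaints or an exacerbation of UC reported by the subjects".
- Section 8.6, headed "Follow-up of subjects withdrawn from treatment", states: "After possible withdrawal, no follow-up of research subjects will take place, except in case of withdrawal for other medical reasons".

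Section 8.5 provides no replacement of withdrawn patients. Section 9.4 follows all adverse events until they have abated or are stable.

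On the endpoint, section 8.1.1 says "As main endpoint, the mean P-SCCAI score for each arm will be determined and compared to each other", at week 8, and adds that "P-SCCAI refers to disease symptoms during the previous week". In the first primary test of section 10.1, "the mean P-SCCAI score between the predicted responders with prebiotics and predicted non-responders with prebiotics will be compared" by t-test or Mann-Whitney test. The second compares prebiotics with placebo within each predicted group. Section 8.1.2 plans P-SCCAI and medication changes to week 60.

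Section 4.4 provides for loss in number only: "Given that the intervention duration is 8 weeks long, followed by a 1 year follow-up, higher dropout rate (30%) is expected".

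**The concern.** The event that removes a patient is a worsening of UC symptoms, and those symptoms are what the primary endpoint measures. A patient who reports a flare at week 5 leaves the study and has no week-8 score, although that score would probably have been among the highest in the arm. The retained mean then describes only those who did not report a flare.

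The heading of section 8.6 concerns stopping treatment, but its text ends follow-up altogether, so stopping the supplement and leaving the study are treated as one. The exception is unclear. Read plainly, *other* medical reasons excludes those listed in 8.4.1. But 8.4 itself calls serious GI complaints urgent medical reasons, so they might fall inside the exception. On neither reading is a week-8 P-SCCAI named.

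At stake is the between-arm difference at week 8, which can come out too small or too large. The P-SCCAI and medication-change endpoints to week 60 suffer the same loss. A medication upgrade counts there as worsening, yet the patients most likely to need one may already have left.

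**Working it through.** **1. The plan's own figures (section 4.4).** Means 3.5 and 2.8, SD 0.5, two-sided α = 0.05, power 0.90. By the normal approximation, n = 2(1.960 + 1.282)² × 0.5² / 0.7² = 10.7, so 11 per group, as stated. The stated 15 follows from 11 × 1.3 = 14.3; dividing by 0.7 gives 15.7, so 16. The 30% allowance is 4.5 of 15 per arm, or 18 of 60, and is not split by reason. It protects numbers but not against loss that depends on the outcome.

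**2. Form of the bias.** Let w be the share of an arm withdrawn for a flare, and g the gap in week-8 score between withdrawn and retained patients. The retained mean is the all-randomised mean minus w·g. For D = non-responder mean minus responder mean (both on prebiotics, planned 0.70):

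bias in D = w(resp)·g(resp) − w(non-resp)·g(non-resp)

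The documents give neither w nor g, so everything below rests on assumptions.

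**3. Loss by week 8.** Loss = 1 − exp(−rate × 8/52). Assumed rates of 0.5 and 1 reported exacerbation per year give 7.4% and 14.3%, or 1.1 and 2.1 of 15. The entry criterion (at least one relapse in two years) describes history and does not forecast a rate.

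**4. Small imbalances.** With equal g in both arms, one extra withdrawal in 15 shifts D by g/15: 0.13 at g = 2 and 0.33 at g = 5. Two extra shift it by 0.27 to 0.67. Either sign is possible.

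**5. Only high scores lost, first comparison.** For normal scores truncated above c, the mean is μ − SD·φ(b)/Φ(b), with b = (c − μ)/SD.

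| SD | Lost above | Lost, non-resp / resp | Observed D | Attenuation |
|---|---|---|---|---|
| 0.5 | 4 | 15.9% / 0.8% | 0.57 | 18.9% |
| 1.0 | 5 | 6.7% / 1.4% | 0.60 | 14.7% |
| 2.0 | 6 | 10.6% / 5.5% | 0.53 | 24.8% |
| 0.5 | 5 | 0.1% / 0.0% | 0.698 | 0.3% |
| 0.5 | 6 | 0.0% / 0.0% | 0.700 | none |

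The first row needs a cut-off inside the 3 to 5 entry range. SDs of 1.0 and 2.0 are not in the protocol.

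**6. Opposite direction.** If responders lose 14.26% and non-responders 7.40%, an observed 0.70 corresponds, among all randomised patients, to 0.70 − 0.0686 × g. That is 0.53, 0.46 and 0.32 at g = 2.5, 3.5 and 5.5.

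**7. Prebiotics versus placebo.** With 14.3% against 7.4% lost and a non-flaring mean of 3.5 assumed in both arms, the hidden difference is 0.0686 × (flare score − 3.5): 0.17, 0.24 and 0.38 at flare scores of 6, 7 and 9. The sign reverses if the rates do, and the bias is 0 at equal rates and scores.

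**8. Effect on the test.** Simulation with 15 per arm, SD 0.5, 4,000 runs, g = 2 to 3:

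- No true difference, 10% lost in each arm: bias about 0, type I error about 0.05.
- No true difference, 20% against 10%: bias 0.20 to 0.30 in size, type I error 0.16 to 0.31.
- True difference 0.70, 10% of responders and 20% of non-responders lost: mean estimate 0.50 to 0.40, power 0.68 to 0.48.
- True difference 0.70, losses reversed: mean estimate 0.90 to 1.00.

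**The case against.** The strongest reply is that the protocol is less restrictive than it looks and that the numbers are hypothetical.

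- *Follow-up* in this protocol also names the week-12 and week-60 periods, at which P-SCCAI is completed. If medical withdrawals fall under the exception in 8.6, those questionnaires might continue. This is a possible reading, but it still leaves week 8 unnamed. The procedures table in section 8.3 is not legible in the text available, so the schedule could not be checked there.
- Section 9.4 is safety follow-up and need not conflict with 8.6. That is fair if the exception covers these patients. On the plain reading, *no follow-up* and following every adverse event to resolution do not fit together.
- Withdrawal for a flare is itself informative. A worst-rank or composite analysis needs no later score, and the Mann-Whitney test is already named. Such an analysis could sit in the analysis plan. It cannot supply a mean P-SCCAI, which is the stated endpoint.
- Some information survives. Withdrawal depends on patient report, so unreported or late worsening is still scored at week 8, and the secondary mixed model can use weeks 0 and 4. The primary tests in 10.1 name only week-8 scores.
- Including scores taken after a medication change favours one estimand. That is a real choice, but collecting the scores does not prevent a supplementary analysis under another.
- The attenuation figures depend on invented cut-offs and SDs. At the protocol's SD with a cut-off of 5 or 6 there is essentially none. At SDs of 1.0 and 2.0 the shifts (0.10 and 0.17) are small beside standard errors of 0.43 and 0.85 at 11 per arm. This stands: the figures show what could happen and do not estimate this trial's bias.

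**Conclusion.** The concern holds. As written, the protocol removes patients from the study for a reported exacerbation and schedules no P-SCCAI afterwards, so primary scores can be missing because of the outcome. This is a matter of data collection, which the analysis plan cannot repair.

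Within one arm, if flaring patients would have scored higher, the retained mean is too low. Between arms, both size and direction are unknown, and the bias is zero when loss times severity is equal. Under the assumptions shown, an imbalance of one or two patients in 15 moves the difference by 0.13 to 0.67 points, against a planned 0.70. Confidence is high on what the text says and on the mechanism; the magnitude is illustrative only. It should be fixed. Whether the clinical withdrawal rule is right is not at issue here.

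**What to change.** Reconcile sections 8.4, 8.4.1 and 8.6 with 8.1.2 and 9.4:

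1. Separate stopping the supplement from leaving the study.
2. State that randomised patients who stop but have not withdrawn consent are still asked for P-SCCAI and medication data at the remaining scheduled time points (weeks 4, 8, 12 and 60).
3. State that these week-8 scores enter the comparison of all randomised patients.
4. Define the other medical reasons in 8.6.

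A sensitivity analysis that assigns a poor outcome to flare withdrawals without a score can be left to the analysis plan.

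The cost is a protocol amendment, consent wording and a few reminders. Questionnaires are completed at home (Summary) using phone apps (section 4.2). Section 11.6 already pays full compensation to patients who withdraw because of adverse events or on medical advice, and 9.4 already foresees contact after an adverse event. The planned sample size is unchanged. The drawback is that some scores will reflect changed medication, which should be recorded and reported. Clinical decisions on stopping the supplement are unaffected.
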